	fluorouracil [5-FU], leucovorin, and oxaliplatin) was superior						
	to that of chemotherapy alone ³ .						
	Given this preliminary efficacy signal, this trial is designed to						
	determine safety and perhaps an even larger signal of						
	efficacy in the first-line setting. FOLFIRINOX is the standard						
	of care for the first-line treatment of patients with advanced						
	disease worldwide and thus supports our first line design in						
	combination with Eryaspase.						
	Eryaspase is a dispersion for infusion of allogenic						
	erythrocytes encapsulating recombinant E. coli L-						
	asparaginase, in a saline preservative solution. Eryaspase is						
	an off-shelf investigational agent. Eryaspase is produced for						
	each individual patient taking into account blood group and						
	phenotype and dose appropriate for body weight.						
	We hypothesize that the addition of Eryaspase to						
	FOLFIRINOX (5-fluorouracil [5-FU], leucovorin, irinotecan,						
	and oxaliplatin) will be safe and demonstrate preliminary						
	signs of efficacy in patients with advanced pancreatic cancer.						
Study Duration	18 months						
Study Center(s)	 Georgetown University, Lombardi Comprehensive Cancer 						
	Center, Washington, DC						

	Page 6 of 46							
	Additional participating centers to be added upon activation							
Objectives	 Primary Objectives The primary objective of this study is to determine the maximum tolerated dose, tolerability and safety of Eryaspase in combination with the dose-modified FOLFIRINOX in patients with newly diagnosed locally advanced or metastatic pancreatic adenocarcinoma Secondary Objectives To determine the objective response rate (ORR), progression-free survival (PFS) and the overall survival (OS) 							
Number of Patients	Approximately 12-19 subjects, subject to determination of MTD							
Diagnosis and Main	Main Inclusion Criteria							
Inclusion and	Patients must be able to understand and willing to sign							
Exclusion Criteria	 an IRB approved written informed consent document. Patients must have histologically or cytologically confirmed pancreatic adenocarcinoma, which is locally advanced, or metastatic. Subject must have received no previous surgery, chemotherapy, radiotherapy or investigational therapy for the treatment of locally advanced or metastatic disease. If a subject has had adjuvant/neoadjuvant therapy for localized disease, tumor recurrence or disease progression must have occurred no sooner than 6 months after completing the last dose of the aforementioned therapies. Patient must have radiographically measurable disease according to RECIST 1.1. Patient must have a life expectancy of ≥ 3 months. Patient must have a life expectancy of ≥ 3 months. Patient must have normal bone marrow and organ function as defined below: Absolute neutrophil count ≥1,500/mcl Platelets ≥100,000/mcl Hemoglobin ≥9.0 g/dL Serum Albumin ≥3.0 g/dL Creatinine should be below the upper limit of normal OR Creatinine clearance ≥ 60 mL/min/1.73 m2 for patients with creatinine levels above institutional normal Plasma antithrombin III ≥ 65%, fibrinogen ≥ 150 mg/dL international normal 							

1.5, and partial thromboplastin time (PTT) <
institutional ULN.
◦ Total bilirubin ≤ 2.0 x institutional ULN
 Patients who have had a stent placed for biliary
obstruction can be included in the study.
 Female subject of childbearing potential must have a
negative urine or serum pregnancy test.
 Women of childbearing potential and men must agree
to use adequate contraception (hormonal or barrier
method of birth control, abstinence) prior to study
entry and for the duration of study participation.
Should a woman become pregnant or suspect she is
pregnant while participating in this study, she must
inform her treating physician immediately.
 Male subjects with a female partner of childbearing
potential must agree to use two adequate methods or
a barrier method plus a method of contraception
Main Exclusion Criteria
 Patient must not have evidence of neuroendocrine
tumor, duodenal adenocarcinoma, or ampullary
adenocarcinoma.
 Patient must not have a history of other malignancy ≤
3 years ago, with the exception of basal cell or
squamous cell carcinoma of the skin, which were
treated with local resection only or carcinoma in situ of
the cervix or ductal carcinoma in situ.
 Patient must not be receiving any other investigational
agents 28 days prior to the screening process.
Patient must not have brain metastases. Such patients
must be excluded from this clinical trial because of
their poor prognosis and because they often develop
progressive neurologic dysfunction that would
confound the evaluation of neurologic and other
adverse events.
 Patient must not have a history of allergic reactions
attributed to compounds of similar chemical or biologic
composition to asparadinase. 5FU oxaliplatin or
irinotecan.
 Patient must not have an uncontrolled intercurrent
illness including, but not limited to ongoing or active
infection symptomatic concestive heart failure
unstable angina pectoris cardiac arrhythmia any
clinically active malabsorption syndrome inflammatory
bowel disease, any condition that increases the risk of
severe irinotecan dastrointestinal toxicity or
psychiatric illness/social situations that would limit
compliance with study requirements

 Has an active autoimmune disease, or a documented history of autoimmune disease or a syndrome that requires steroids or immunosuppressive agents. Subjects with vitiligo or resolved childhood asthma/atopy would be an exception to this rule. Has had an allogeneic tissue/solid organ transplant. Has received or will receive a live vaccine within 30 days prior to the first administration of study medication. Seasonal flu vaccines that do not contain live virus are permitted Has known active Hepatitis B or C. Patient must not be pregnant and/or breastfeeding. 						
his will be a single-arm, multi-center, open-label phase 1 tudy. The standard 3+3 design will be used to determine						
ne maximum tolerated dose (MTD) from 4 possible dose evels.						
nFOLFIRINOX dosing will include 5-fluorouracil 2400 mg/m² ver 46 hours, oxaliplatin 85 mg/m², Irinotecan 150 mg/m²						
plus Eryaspase 75 Units/kg administered on day 1 every 14 days. We will dose escalate to Eryaspase 100 units/kg and						
lso build in 2 dose reduction levels.						
Safety assessments include adverse events, physical xamination abnormalities, vital signs, and clinical laboratory ests (including blood chemistry, hematology, and oagulation panel).						
emographics and Baseline Characteristics						
 All subject baseline characteristics and demographic data (age, sex, race, ethnicity, weight, height, body mass index, physical examination abnormalities, medical history, previous [within 6 months of screening]) and concomitant medications at study entry will be listed by study center and subject number and summarized with appropriate summary statistics. 						
 stablishing Maximum Tolerated Dose (MTD) The standard phase I 3+3 design of dose 						
escalation will be used to determine the maximum						
tolerated dose (MTD) from 5 possible dose levels, including at most 1 escalation level and 3 de-						

	patients experience a dose-limiting toxicity (DLT) during the first cycle. If 0 or 1 of 6 patients in Dose Level 1 experience DLT during the first cycle, Dose Level 1 will be presumed to be the MTD. Additional 6 patients will be included at the MTD level.
Sa	afoty Analysis
38	 All subjects who are enrolled and received at
	 All subjects who are enrolled and received at least one dose of study medication will be
	included in the safety population
	 The primary safety endpoint is the subject
	incidence of Grade 3 or 4 adverse events. The
	number and percentage of all subjects who
	experience any adverse events (AEs) (Grade 1
	through 4), serious adverse events (SAEs), or
	clinically significant abnormal laboratory results
	will be reported.
	Other safety endpoints include:
	 Clinically significant changes from baseline
	in all safety laboratory parameters;
	 Clinically significant changes from baseline
	in vital signs;
	 Incidence and type of clinically significant ECC observabilities
	ECG abhormaillies.
	 All clinical safety and tolerability data will be listed by subject and will be summarized. Treatment
	emergent adverse events will be listed and
	summarized by System Organ Class by
	relatedness, and by maximum severity. Serious
	adverse events and adverse events leading to
	withdrawal will be listed and summarized.
	Individual vital signs and change from baseline in
	vital signs will be listed by subject, and study visit,
	and summarized descriptively. Laboratory data
	(actual values and change from baseline) will be
	listed by subject and study
Ef	ficacy Analysis
	 Analysis of secondary endpoints: Due to small
	sample sizes and dose heterogeneity, no
	statistical tests of hypotheses are planned for the
	summarized Overall survival and progression-
	free survival will also be summarized as
	preliminary estimates of efficacy in this patient
	population using a Kaplan Meier estimator/curve.

2. Schedule of Events (Table 1)

			Table 1						
			Treatment (28-day/4-week cycles, ±1-day)						
Study Procedures	Screening Period up to 3 weeks	Up to 5-8 days prior to C1D1	C1D1	C1D8	C1D15	C1D22	D1 and D15 on subsequent cycles	End of Treatment Visit (+/- 7 days)	Follow up (every 8 wks, ± 1 week)
Informed consent	Х								
Eligibility criteria	Х		Х						
Demography	Х								
Medical history	Х								
Concomitant Medications Collection	Х		Х		Х		Х		
Physical exam (including height [screening only] and weight)	х		х	х	х	х	Х	Х	
Vital signs (temperature, BP, and heart rate)	Х		Х	Х	Х	Х	Х	Х	
Performance status [1]	х		Х	х	х	х	Х	х	
12-Lead ECG	Х		X[2]		X[2]			Х	
Radiological assessments (CT or MRI) [3]	х	X (every 8	weeks [±3	days] fro	om time c	of enrollm	nent until disease	progression, or death)	
AEs/SAEs [14]	X (collected from the time of informed consent until 30 days after the last study treatment)								
Blood phenotype [4]	X[4]								
Prescription with current weight		X[5]	X[5]		X[5]		X[5]		
Irregular antibody screening test (IAST) [6]	X[6]		X[6]		X[6]		X[6]		
Pre-eryaspase dose complete compatibility test [7]			X[7]		X[7]		X[7]		
Eryaspase administration [8]			X[8]		X[8]		X[8]		
FOLFIRINOX			Х		Х		Х		
Hematology, biochemistry, and coagulation panels; CA19-9 [9]	X[9,10]		х		х		Х	Х	
Pregnancy test, for patients of childbearing potential [11]	х		Х		х		Х	х	
Survival follow-up									X[13]
Subsequent anti-cancer treatments									х

Tables abbreviations and legends:

D=Day; BP=blood pressure; ECG=electrocardiogram; CT=computed tomography; MRI=magnetic resonance imaging; IAST=irregular antibody screening test; CA19-9=cancer antigen 19-9; ASPNase = Asparaginase. [1] According to the Eastern Cooperative Oncology Group (ECOG)

[2] Performed pre-dose Cycle 1 Day 1 and Day 15

[3] Radiological assessment (CT C/A/P) to be completed within 3 weeks of screening and then every 8 weeks (±3 days) from the time of enrolment until disease progression or until withdrawal from the study treatment, or death, using the same method throughout.

[4] A complete erythrocyte phenotype (including D, C, E, c, e, and K antigens), ABO blood group status, and

Rhesus factor, all assessed on 2 separate samples (can be collected on the same day), to be done at least 5 working days before the first Eryaspase infusion. For group A and AB patients, sub-grouping A1/A1B and A2/A2B is required. If A subgroup, screening of anti-A1 antibodies (Indirect Coombs method) should be performed for A2 and A2B patients. The A2 and A2B patients will require anti-A1 antibodies screening before each administration along with IAST and documented on IAST form.

[5] A prescription form indicating the patient's identifiers as well as his/her current weight, the investigator's recipient of the product, and the place and time of the delivery must be sent as soon as possible once the Eryaspase infusion is scheduled, and at the latest 5 working days prior to each Eryaspase infusion. Exact instructions are provided by the IMP Manual.

[6] The IAST blood sample and results must be completed within 72 hours prior to each Eryaspase administration and a report provided to the sponsor as soon as possible prior to each Eryaspase infusion.

[7] This should be performed by the blood bank at the local institution. If not compatible, eryaspase must not be administered and the sponsor should be notified immediately. A collection of additional blood sample will be required for further investigation.

[8] A ±1-day window is permitted for Eryaspase or FOLFIRINOX dosing for scheduling purposes.

[9] Laboratory tests to be performed at the local laboratory as follows: Hematology: Complete blood count with differential (hemoglobin, hematocrit, erythrocyte count, white blood cell (WBC) count, neutrophils, lymphocytes, monocytes, eosinophils, basophils, mean cell hemoglobin (MCH), mean cell hemoglobin concentration (MCHC), mean corpuscular volume, reticulocytes and platelet count). Serum Chemistry: Sodium, potassium, bicarbonate, calcium, chloride, magnesium, creatinine, albumin, total bilirubin (direct and indirect), alanine aminotransferase, aspartate aminotransferase, alkaline phosphatase, gamma-glutamyl transferase, , glucose, urea, amylase, lipase, inorganic phosphorus, and total protein; Coagulation parameters – international normalized ratio (INR), Partial thromboplastin time, fibrinogen, plasma antithrombin III, D-dimer. Tumor marker: CA19-9

[10] Baseline labs to be collected within the first 21 days of the screening period

[11] For patients of childbearing potential, serum pregnancy test to be performed during the screening period and at End of Treatment and urine/serum pregnancy test to be performed prior to dosing of any chemotherapy agent
[13] Survival follow to be conducted by phone, visit, or medical records review every 8 weeks (± 1 week) from end of treatment visit until patient's death, loss to follow up, or study closure. Subsequent therapy should be collected during this follow up.

Additional lab tests may be required (e.g., weekly monitoring per standard practice or label requirements should be followed) and should be reported if clinically significant

[14] SAEs are not required to be reported until after they received the first dose.

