5.5 Dose Limiting Toxicities (DLT)

To the extent possible, any adverse events that are deemed to study drug-related and are ongoing at end of treatment will be followed up to resolution or until a determination is made that the unresolved event is stable.

In general, Grade 1 and 2 toxicities do not require any dose modification for any of the chemotherapy agents or for Eryaspase. However, appropriate supportive care will be provided for the management of drug-related toxicities.

Hematologic DLT is defined as any of the following that occurs during the first cycle (total of approximately 28 days) of treatment that is attributed as possibly, probably, or definitely related to Eryaspase alone or the combination of Eryaspase and FOLFIRINOX:

- Grade 4 neutrophil count decrease > 7 day duration
- Febrile neutropenia \geq Grade 3 of any duration
- Grade 3 or Grade 4 platelet count decrease
- Any Grade 4 platelet count decrease with bleeding

Non-hematologic DLT is defined as any grade 3 or grade 4 adverse event, based on NCI CTCAE that occurs during the first cycle (total of approximately 28 days) of treatment that is considered possibly, probably, or definitely related to Eryaspase alone or the combination of Eryaspase and FOLFIRINOX with the following specific exceptions:

- Grade 3 or 4 AST, ALT, alkaline phosphatase, or total bilirubin due to biliary obstruction or infection
- Grade 3 or 4 nausea, vomiting, or diarrhea resolved with maximal supportive care within 7 days
- Grade 3 mucositis resolved with supportive care
- Grade 3 fatigue lasting less than 7 days
- Grade 3 or 4 laboratory abnormalities that are not clinically significant or do not require any clinical intervention.

Any treatment-related toxicity that results in treatment delay for > 21 days cumulatively during the first cycle or > 14 days cumulatively during the second cycle will be considered a DLT, and the patient will be removed from the study. If the treatment delay during the first cycle is due to reasons other than treatment-related toxicity, the patient will be replaced as the subject will be considered to be inevaluable for DLT.

5.6 **Dose modification**

Dose reduction or modification are only allowed after passing the 28 days DLT period. Recommended mFOLFIRINOX dose modifications are listed in Table 3, however modification may follow investigator or institutional guidelines. Modifications may be made to any or all chemotherapy agents, per investigator discretion.

Table 3

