5.11 Study Pause Criteria

The protocol will be paused with any criteria below being met:

- Any death (other than due to progressive disease)
- The occurrence of 2 or more grade 4 events

6. Study Population

6.1 Inclusion Criteria

Patients must meet all of the following inclusion criteria to participate in this study:

- 6.1.1 Patient must be able to understand and willing to sign an IRB approved written informed consent document.
- 6.1.2 Patient must have histologically or cytologically confirmed pancreatic adenocarcinoma, which is locally advanced, unresectable, or metastatic.
- 6.1.3 Patient must have received no previous surgery, chemotherapy, radiotherapy or investigational therapy for the treatment of locally advanced or metastatic disease.
- 6.1.4 If a patient has had adjuvant/neoadjuvant therapy for localized disease, tumor recurrence or disease progression must have occurred no sooner than 6 months after completing the last dose of the aforementioned therapies.
- 6.1.5 Patient must have radiographically measurable disease according to RECIST 1.1
- 6.1.6 Patient must be > 18 years of age.
- 6.1.7 Patient must have a life expectancy of \geq 3 months.
- 6.1.8 Patient must have an ECOG performance status \leq 1.
- 6.1.9 Patient must have normal bone marrow and organ function as defined below:

0	Absolute neutrophil count	> 1,500/mcl
0	Platelets	> 100,000/mcl
0	Hemoglobin	> 9.0 g/dL
0	Serum Albumin	>3.0 g/dL

- Creatinine should be below the upper limit of normal OR Creatinine clearance (eGFR) >60 mL/min/1.73 m2 for patients with creatinine levels above institutional normal
- Plasma antithrombin III > 65%, fibrinogen > 150 mg/dL (1.5g/L), international normalized ratio (INR) < 1.5, and partial thromboplastin time (PTT) < institutional ULN.
- Total bilirubin \leq 2.0x institutional ULN
- 6.1.10 Patients who have had a stent placed for biliary obstruction can be included in the study.
- 6.1.11 Female subject of childbearing potential must have a negative urine or serum pregnancy test.

- 6.1.12 Women of childbearing potential and men must agree to use adequate contraception (hormonal or barrier method of birth control, abstinence) prior to study entry and for the duration of study participation. Should a woman become pregnant or suspect she is pregnant while participating in this study, she must inform her treating physician immediately.

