- 6.1.13 Male subjects with a female partner of childbearing potential must agree to use two adequate methods or a barrier method plus a method of contraception

6.2 Exclusion Criteria

Patients meeting any of the following exclusion criteria will not be able to participate in this study:

- 6.2.1 Evidence of neuroendocrine tumor, duodenal adenocarcinoma, or ampullary adenocarcinoma.
- 6.2.2 History of other malignancy \leq 3 years ago, with the exception of basal cell or squamous cell carcinoma of the skin, which were treated with local resection only or carcinoma in situ of the cervix of ductal carcinoma in situ.
- 6.2.3 Receiving any other investigational agents 28 days prior to the screening process.
- 6.2.4 Patient with evidence of brain metastases. Such patients must be excluded from this clinical trial because of their poor prognosis and because they often develop progressive neurologic dysfunction that would confound the evaluation of neurologic and other adverse events.
- 6.2.5 History of allergic reactions attributed to compounds of similar chemical or biologic composition to asparaginase, 5FU, oxaliplatin, or irinotecan.
- 6.2.6 Any uncontrolled intercurrent illness including, but not limited to, ongoing or active infection, symptomatic congestive heart failure, unstable angina pectoris, cardiac arrhythmia, any clinically active malabsorption syndrome, inflammatory bowel disease, any condition that increases the risk of severe irinotecan gastrointestinal toxicity, or psychiatric illness/social situations that would limit compliance with study requirements
- 6.2.7 Has an active autoimmune disease, or a documented history of autoimmune disease or syndrome that requires steroids or immunosuppressive agents. Subjects with vitiligo or resolved childhood asthma/atopy would be an exception to this rule.
- 6.2.8 History of abdominal fistula, gastrointestinal perforation, peptic ulcer, or intraabdominal abscess within 6 months prior to randomization.
- 6.2.9 Has had an allogeneic tissue/solid organ transplant.
- 6.2.10 Has received or will receive a live vaccine within 30 days prior to the first administration of study medication. Seasonal flu vaccines that do not contain live virus are permitted
- 6.2.11 Has known active Hepatitis B or C.
- 6.2.12 Patient is pregnant and/or breastfeeding.
- 6.2.13 Known to be HIV-positive on combination antiretroviral.

6.3 Randomization and Method of Treatment Assignment

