9.1.1 Eryaspase

Eryaspase is a dispersion for infusion of allogeneic erythrocytes encapsulating recombinant *E. coli* L asparaginase, in a saline preservative solution. Eryaspase is an off-shelf investigational agent. Eryaspase is produced for each individual patient taking into account blood group and phenotype and dose of ASNase appropriate for body weight.

Eryaspase was previously studied as a single agent in twelve patients with pancreatic cancer. No patient experienced dose limiting toxicities at any dose level. One patient experienced grade 3 lymphopenia one patient experienced grade 1 allergic pruritus. Eryaspase was later studied in combination with chemotherapy in 93 patients with pancreatic cancer, in comparison to the control arm of chemo alone grade 3 and 4 hematological adverse event occurred with similar frequency between treatment arms. The most common adverse events were asthenia (68.8%), nausea (62.4%, anemia (45.2%), thrombocytopenia (43%), emesis (44.1%), abdominal pain (35.5%) and diarrhea (39.8%), however these are most likely secondary to chemotherapy²⁶.

In previous studies of Eryaspase in acute lymphocytic leukemia the most common adverse events were thrombocytopenia (13.6%), elevated transaminases (13.6%), anemia (8.8%), neutropenia (6.4%), and leukopenia (5.6%)²⁶.

Further information can be found in the current version of the Eryaspase Investigator's Brochure.

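### Eligibility sets no AST or ALT limit and section 5.5 has no rule for an abnormal baseline, so a raised transaminase in Cycle 1 can be scored as a DLT or dismissed

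*Combined protocol and SAP*

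**What the plan says.** **Entry.** The synopsis (Main Inclusion Criteria) and section 6.1.9 each state that "Patient must have normal bone marrow and organ function as defined below". A closed list follows in both places: neutrophils, platelets, hemoglobin, albumin, creatinine or its clearance, antithrombin III, fibrinogen, INR, PTT and total bilirubin. The bilirubin limit is "2.0x institutional ULN". AST and ALT appear in neither list. Section 6.1.10 adds "Patients who have had a stent placed for biliary obstruction can be included in the study". The nearest hepatic exclusion is 6.2.11, "Has known active Hepatitis B or C".

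**Measurement.** Table 1, footnote [9], includes "alanine aminotransferase, aspartate aminotransferase, alkaline phosphatase" in the chemistry panel, which is drawn at screening and on C1D1. Table 1 also has an eligibility check at both visits.

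**DLT rule.** Section 5.5 reads "Non-hematologic DLT is defined as any grade 3 or grade 4 adverse event, based on NCI CTCAE that occurs during the first cycle". The event must be at least possibly related to Eryaspase or the combination. One exception covers "Grade 3 or 4 AST, ALT, alkaline phosphatase, or total bilirubin due to biliary obstruction or infection". Another covers Grade 3-4 laboratory findings that lack clinical importance or call for no intervention.

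**Adverse event rule.** Section 8.3.1 classes adverse events reported before the first dose as pretreatment events. It treats a laboratory abnormality as an adverse event only if it leads to discontinuation, needs treatment, or the investigator judges it to be one. It also counts worsening of a pre-existing condition as an adverse event.

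**Decision rule.** Under 5.3, two DLTs put a level above the MTD. Under 5.4, the MTD is the highest level with at most 1 DLT in 6.

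**The concern.** The primary result depends on 0, 1 or 2 DLTs among three to six patients, so each DLT call must be reproducible. For transaminases it may not be. The entry criteria admit metastatic disease and stented patients, so raised enzymes at entry are foreseeable. Section 9.1.1 gives elevated transaminases at 13.6% in the leukemia studies, level with thrombocytopenia as the most frequent event listed there.

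Suppose a patient enters with markedly raised enzymes and the value persists or worsens in Cycle 1. One investigator may call it possibly related and count it. Another may call it pre-existing, or clinically unimportant, and not count it. Section 5.5 does not settle the matter, and enrollment is competitive across sites (6.5.2). A false DLT can reject a tolerable level. A dismissed true DLT can help an intolerable one through. The same gap also admits patients at higher hepatic risk to an untested combination.

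The protocol uses this reasoning elsewhere: 6.2.4 excludes brain metastases partly because they would confound the assessment of adverse events.

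**Working it through.** **Step 1: can such a patient enter?** Yes. A patient with severely raised AST or ALT, bilirubin within the limit, and no known active hepatitis B or C fails no numeric criterion. The list appears in full twice with the same omission.

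**Step 2: is the Cycle 1 score determined?** No.

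- Timing: 8.3.1 sets aside adverse events reported before dosing. A raised screening value need not be recorded as an adverse event, and worsening counts as a new event.
- Relatedness: 5.5 needs only a possible relation, but 8.3.3 defines only Related and Not Related.
- Exceptions: the first covers biliary obstruction and infection, not metastases or other causes. The second is a judgment with no reference to baseline.
- Grading: 8.3.1.1 cites CTCAE 5.0 without reproducing it, so how it treats an abnormal baseline cannot be checked here.

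**Step 3: what does one misclassified patient do?** The plan gives no operating characteristics and no expected DLT rate, so true DLT rates p of 10%, 20% and 30% are assumed. Let q = 1 − p.

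Under the 5.3 rule, a level is passed on 0/3, or on 1/3 followed by 0/3:

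- All calls correct: P(reject) = 1 − q³ − 3pq⁵. At 10%: 1 − 0.729 − 0.177 = 0.094. At 20%: 1 − 0.512 − 0.197 = 0.291.
- One of the first three wrongly counted: the other five must all be DLT-free, so P(reject) = 1 − q⁵. At 10%: 1 − 0.590 = 0.410. At 20%: 1 − 0.328 = 0.672.
- One of the first three cannot register a DLT: P(reject) = 1 − q² − 2pq⁴. At 10%: 1 − 0.810 − 0.131 = 0.059. At 20%: 1 − 0.640 − 0.164 = 0.196. This is an extreme case, because only that patient's hepatic events could be dismissed as pre-existing.

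| True DLT rate (assumed) | Correct | One wrongly counted | One fully masked |
|---|---|---|---|
| 10% | 0.094 | 0.410 | 0.059 |
| 20% | 0.291 | 0.672 | 0.196 |
| 30% | 0.506 | 0.832 | 0.366 |

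**Step 4: partial masking.** Take p = 1/3 and assume that half of one patient's DLT risk is hepatic and is dismissed, so that patient's rate is 1/6. Acceptance with correct calls is (2/3)³ + 3(1/3)(2/3)⁵ = 0.296 + 0.132 = 0.428. With masking it is 0.370 + 0.444 × 0.296 = 0.502. The one-half share is an assumption. No masking gives 0.428; full masking at this rate gives (2/3)² + 2(1/3)(2/3)⁴ = 0.444 + 0.132 = 0.576.

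**Step 5: if six patients are required, as 5.4 implies at the MTD.** With correct calls, P(at least 2 of 6) is 0.114, 0.345 and 0.580 at the three rates. With one wrongly counted it is again 1 − q⁵: 0.410, 0.672 and 0.832. With one fully masked it is 0.081, 0.263 and 0.472. The pattern is the same.

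**Step 6: the missing probability.** Let w be the chance that one of the first three patients enters with raised enzymes and is wrongly counted. The unconditional rise in rejection is w × (0.410 − 0.094) = 0.316w at 10%, w × (0.672 − 0.291) = 0.381w at 20%, and w × (0.832 − 0.506) = 0.326w at 30%. The documents give no value for w. The rise can lie anywhere from zero to the full difference.

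**The case against.** A reader might infer that Grade 3-4 AST or ALT is simply a DLT, so that a patient entering at that grade arrives already counted. The documents do not support this. Section 5.5 names AST and ALT only in an exception. A value counts only through the general rule: it must be an adverse event in Cycle 1, at least possibly related, and outside two exceptions. Section 8.3.1 puts events reported before dosing in a separate class. Stented patients are also the group that the obstruction exception addresses.

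Further points against:

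- The 13.6% comes from leukemia, with no grade stated. For the 93 pancreatic cancer patients on Eryaspase plus chemotherapy, 9.1.1 does not list transaminases among the most common events.
- The liver is not unscreened: bilirubin, albumin and coagulation are limited, 6.2.6 excludes uncontrolled intercurrent illness, and records are reviewed centrally before treatment (6.5.2, 7.1).
- The large percentages assume both entry and misclassification.
- A baseline rule in 5.5 alone would prevent false DLTs without excluding anyone.

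Most of this stands and narrows the point. What it leaves open is the value that persists or worsens in Cycle 1, is called possibly related, and has no stated baseline reference. Central review can apply only the criteria as written, and these contain no transaminase limit. A baseline rule alone would also leave a patient who starts at the grade 5.5 can count with little room to register a true hepatic DLT, and would not address who is dosed.

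**Conclusion.** The point holds as an ambiguity in how a Cycle 1 transaminase elevation is scored, created by the missing entry limit together with the missing baseline rule. It does not show that the MTD will be wrong, or that a high value before dosing is itself a DLT.

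The cost of one wrong call is large: rejection of a level goes from 9% to 41% at an assumed true DLT rate of 10%, and from 29% to 67% at 20%. The error can also run the other way: with one patient fully masked, rejection falls from 29% to 20% at a true rate of 20%. All of these figures rest on assumed DLT rates and on one misclassified patient among the first three. They must not be read as expected error rates for the trial, because the documents do not say how often such a patient would enter or be misjudged. It is a cheap improvement, worth making because it protects both the count and the patients dosed.

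**What to change.** Reconcile the synopsis and 6.1.9 with 5.5 and 8.3.1:

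1. Add an AST and an ALT entry limit to both lists. The sponsor sets the values, so that no patient enters already at the grade that 5.5 can count. Apply them at the screening and C1D1 eligibility checks already in Table 1.
2. State in 5.5 how an abnormal baseline AST or ALT is handled when a Cycle 1 value is assessed as a possible DLT, consistently with the pretreatment and laboratory rules in 8.3.1. The content of that rule is for the sponsor. With entry limited as in item 1, a requirement that the grade has risen since C1D1 would add nothing for Grade 3 values. The statement is needed for values that are raised at entry but below that grade.

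The cost is a few lines of amendment and no new tests, since both enzymes are already drawn at screening and C1D1. The downside is that a few patients with raised enzymes are excluded or deferred.
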